#### RESCUE MEDICATION USE FOR ERP

Participants will be asked daily whether they used the rescue medication in the past 24 hours to treat their ERP. If yes, then number of tablets will be documented.

The secondary efficacy variables of rescue medication use for ERP are:

- Change from BC to TRC1, TRC2, and TRC3 in the mean number of tablets of rescue medication taken for ERP
- Change from BC to TRC1, TRC2, and TRC3 in the proportion of days participant has taken rescue medication for ERP

The mean number of tablets of rescue medication for ERP will be calculated for each cycle as the total number of tablets of rescue medication for ERP reported during the cycle, divided by the number of days during the cycle when a value was reported.

The proportion of days participant has used rescue medication for ERP will be calculated for each cycle as the total number of days participant has used ANY rescue medication for ERP, divided by the number of days during the cycle when a value was reported.

#### PGI-S AND PGI-C SCORE

The PGI-S is a single item measuring the overall severity of pelvic pain over the past 7 days on a 4-point Likert-type scale (0=None, 1=Mild, 2=Moderate, 3=Severe) where lower values represent a better outcome.

The PGI-C is a single item measuring the change in pelvic pain since the start of the study treatment on a 5-point scale: 0=much better, 1=a little better, 2=no change, 3=a little worse, and 4=much worse.

The secondary efficacy variables of PGI-S and PGI-C are:

- Change in PGI-S Score from V4 to Phone Contact CCI
- Percentage of participants with any improvement on the PGI-C at TRC1, TRC2, and TRC3
- Percentage of participants with any improvement on the PGI-S at TRC1, TRC2, and TRC3

Participants with any improvement on the PGI-C is defined as a PGI-C score of 0 or 1 (0=much better, 1=a little better).

Participants with any improvement on the PGI-S is defined as an improvement from baseline of at least one step in the score.

#### ENDOMETRIOSIS HEALTH PROFILE-30 (EHP-30)

The EHP-30 is a validated disease specific patient-reported outcome (PRO) instrument measuring the HRQoL of women with endometriosis. The EHP-30 consists of 30 items covering the following domains: pain (11 items, Q1-Q11), controls and powerlessness (6 items, Q12-Q17), emotional well-being (6 items, Q18-Q23), social support (4 items, Q24-Q27), and self-image (3 items, Q28-Q30). Each item is answered on a 5-point Likert-type scale (0=never, 1=rarely, 2=sometimes, 3=often, 4=always).

The secondary efficacy variables of EHP-30 are:

- Change from CCI (BC) to CCI (TRC3) in the EHP-30 domain pain (11 items, Q1-Q11)
- Change from CCI (BC) to CCI (TRC3) in the EHP-30 domain control and powerlessness (6 items, Q12-Q17)
- Change from CCI (BC) to CCI (TRC3) in the EHP-30 domain emotional well-being (6 items, Q18-Q23)
- Change from CCI (BC) to CCI (TRC3) in the EHP-30 domain social support

(4 items, Q24-Q27)

- Change from CCI (BC) to CCI (TRC3) in the EHP-30 domain self-image (3 items, Q28-Q30)

Scores for each domain are transformed from raw scores to range from 0 (indicating the best health status) to 100 (worst health status). The domain score is calculated as the total of raw scores for each item in the domain divided by the total possible raw score times 100. Lower scores indicate better QoL.

#### 8.4.2. Intercurrent Event Handling and Data Imputation for Secondary Efficacy Endpoints

See section 8.1.6, no missing data will be imputed for the secondary efficacy endpoints.

#### 8.4.3. Analysis of Secondary Efficacy Endpoint(s)

##### ANALYSIS OF ENDOMETRIOSIS-RELATED PAIN (DYS, NMPP, AND DYSPAREUNIA) SCORES

Similar analysis for the primary efficacy variable described in Section 8.3.5 using longitudinal model will be performed for change from BC to TRC3 in the mean DYS score, the mean NMPP score, and the mean dyspareunia score.

Similar sensitivity/supplementary analysis as for the primary efficacy variable described in Section 8.3.6 and 8.3.7 will be performed for change from BC to TRC3 in the mean CCI DYS score and the mean CCI NMPP score.

For the analysis of change from BC to mean CCI DYS score, the sensitivity analysis will exclude cycles with <2 CCI DYS scores.

For the analysis of change from BC to mean CCI NMPP score, the sensitivity analysis will exclude cycles with <10 CCI NMPP scores.

Similar supplementary analyses as for the primary efficacy variable described in Section 8.3.7 will be performed for change from BC to TRC3 in mean dyspareunia score. The sensitivity analysis described in Section 8.3.6 based on the PP analysis set will also be performed.

##### ANALYSIS OF RESCUE MEDICATION USE FOR ERP

Similar analysis for the primary efficacy variable described in Section 8.3.5 using a

longitudinal model will be performed for change from BC to TRC3 in the mean number of tablets of rescue medication for ERP and the proportion of days participant has used rescue medication for ERP. Similar supplementary analyses as for the primary efficacy variable described in Section 8.3.7 will be performed for change from BC to TRC3 in the mean number of tablets of rescue medication for ERP and the proportion of days participant has used rescue medication for ERP.

#### ANALYSIS OF PGI-S

Change from V4 to Phone Contact CCI in the PGI-S Score will be summarized in a shift table by treatment group and visit.

#### ANALYSIS OF PGI-C

The number and percentage of participants with any improvement on the PGI-C at phone contact CCI will be summarized by treatment group and visit.

Results will be expressed as the number and percentage of subjects with any improvement on the PGI-C.

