**Table 1: Objectives and Endpoints (as described in the study protocol)**

Objectives	Endpoints
Primary Endpoints The following primary efficacy endpoint will be assessed comparing Group A (CCI BID), B (CCI BID), C (CCI BID) with Group D (Placebo)	

 
To evaluate the efficacy of 3 dose levels of OG-6219 (Group A, B, C) versus Placebo (Group D) in reducing OPP during TRC3, as measured by a NRS in the eDiary
 
	
 
Change from BC to TRC3 in the mean OPP scorea
 

The following primary safety endpoints will be assessed for Group A (CCI BID), B (CCI BID), C (CCI BID) and Group D (Placebo)	

 
To evaluate the safety and tolerability of OG-6219
 
	
 
Proportion of participants who experienced any AEs/SAEs
 
Abnormalities in clinical laboratory assessments, vital signs, and physical examination
 
Proportion of participants who prematurely discontinued study treatment due to AEs/SAEs
 

Secondary Efficacy Endpoints The following secondary endpoints will be assessed comparing Group A (CCI BID), B (CCI BID), C (CCI BID) with Group D (Placebo)	
1. To evaluate the efficacy of 3 dose levels of OG-6219 (Groups A, B, C) versus Placebo (Group	
 
Change from BC to TRC3 in the mean DYS score
 

D) in reducing DYS during TRC3, as measured by a NRS in the eDiary	
2. To evaluate the efficacy of 3 dose levels of OG-6219 (Groups A, B, C) versus Placebo (Group D) in reducing NMPP during TRC3, as measured by a NRS in the eDiary	
 
Change from BC to TRC3 in the mean NMPP score
 

3. To evaluate the efficacy of 3 dose levels of OG-6219 (Group A, B, C) versus Placebo (Group D) reducing dyspareunia during TRC3, as measured by a NRS in the eDiary	
 
Change from BC to TRC3 in the mean dyspareunia score
 

4. To evaluate the daily use of Sponsor provided rescue medication taken for ERP at TRC1, TRC2, and TRC3	
 
Change from BC to TRC1, TRC2, and TRC3 in the mean number of tablets of rescue medication for ERP
 
Change from BC to TRC1, TRC2, and TRC3 in the proportion of days participant has used rescue medication for ERP
 

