5. To evaluate the change in the PGI-S Score at different time points	
 
Change in PGI-S Score from C to Phone Contact CCI
 

6. To evaluate the change in the PGI-C Score in different time points	
 
Percentage of participants with any improvement on the PGI-C at TRC1, TRC2, and TRC3
 

7. To evaluate the change in the EHP-30 domains (CCI ) from BC to TRC3	
 
Change from BC to TRC3 in the EHP-30 Domain Scores
 

Secondary Safety Endpoints	
8. To assess the incidence of clinically significant b changes from V1 to C in bone biomarkers: 	
 
Mean change from V1 to C in bone biomarker levels
 

9. To assess the incidence of any clinically significant b changes in laboratory parameters from V1 to CC 	
 
Proportion of participants with clinical parameters of significance from V1 to CCI
 

10. To assess vaginal bleeding pattern over the 3 menstrual cycles (TRC1, TRC2, and TRC3) as captured in the eDiary	
 
Mean change from BC to TRC1, TRC2, TRC3 in the number of days on period and number of days with irregular vaginal bleeding/spotting
 

11. To assess any potential change in the ECG parameters at CCI	
 
ECG parameter changes at CCI
 

Secondary PD / PK Endpoints	
12. To assess the change from CCI in serum hormone c concentrations	
 
Mean change from CCI in serum hormone levels
 

13. To assess any difference in serum hormone c concentrations at C between active treatment versus placebo	
 
Serum hormone levels at V5 comparing Group A (CCI BID), B (CCI BID), C (CCI BID) with Group D (Placebo)
 

Version Date: 09JUN2025

- Treatment Cycle 1 is the period between the first day of menses associated with treatment start (C) to the day prior to the first day of next menses, regardless of number of days.
- Treatment Cycle 2 is the period between the first day of second menses after end of BC to the day prior to first day of next menses, regardless of number of days.
- Treatment Cycle 3 or EOT is the period between the first day of third menses after end of BC to either end CCI on study treatment, whichever occurs first.

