#### ANALYSIS OF EHP-30

The five EHP-30 Domain scores will be summarized by descriptive statistics of observed data and change from baseline values.

A similar analysis for the primary efficacy variable described in Section 8.3.7 using ANCOVA will be performed for change from baseline in each EHP-30 Domain score.

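### PGI-C and PGI-S are secondary endpoints to be compared with placebo, but the SAP specifies only descriptive output and no inferential comparison

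*SAP*

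**What the plan says.** **What is promised**

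- Protocol Table 1 and SAP Table 1 open the secondary efficacy block with "The following secondary endpoints will be assessed comparing Group A", and go on to name Groups B and C and placebo (Group D). PGI-S and PGI-C are items 5 and 6 in that block. The PGI-C endpoint reads "Percentage of participants with any improvement on the PGI-C at TRC1, TRC2, and TRC3".
- Protocol 9.1.1 says secondary endpoints are tested and nominal p-values given. SAP 8.1.7 says each dose is compared with placebo pairwise.
- SAP section 3 builds the secondary efficacy estimands on the same principle as the primary one, whose summary measure is a difference from placebo.

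**What is planned**

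- SAP 8.4.1 lists "Change in PGI-S Score from V4 to Phone Contact CCI" (later visits redacted) and the PGI-C percentage. It adds a variable that is not in Table 1: "Percentage of participants with any improvement on the PGI-S at TRC1, TRC2, and TRC3".
- SAP 8.4.3, PGI-S: the change "will be summarized in a shift table by treatment group and visit".
- SAP 8.4.3, PGI-C: "Results will be expressed as the number and percentage of subjects with any improvement on the PGI-C".
- SAP 8.4.3 has no entry for improvement on the PGI-S. The general rule in 8.1.1, counts and percentages for categorical and ordinal variables, is all that applies.
- SAP section 10 reports no changes to the protocol-planned analyses.

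**The concern.** The promise and the plan do not match. A programmer who follows 8.4.3 to the letter produces no effect measure, confidence interval or test against placebo for any PGI variable. Every other secondary efficacy endpoint gets one.

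Two things are at stake. Readers would have to judge the patients' own global ratings from percentages without a planned estimate of the treatment difference. And if the sponsor does want the comparison that Table 1 announces, SAP section 2 requires any analysis not described in the SAP to be identified as post-hoc or unplanned. A comparison announced in the protocol would then carry that label.

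**Working it through.** **Step 1. The secondary efficacy endpoints side by side (SAP 8.4.3)**

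| Endpoint | Planned analysis | Difference from placebo with CI? |
|---|---|---|
| DYS, NMPP, dyspareunia | MMRM as for the primary, plus ANCOVA | Yes |
| Rescue medication (tablets, days) | MMRM, plus ANCOVA | Yes |
| EHP-30 domains | "ANCOVA will be performed for change from baseline in each EHP-30 Domain score" | Yes |
| PGI-S change | Shift table | No |
| PGI-S improvement | No entry; counts rule in 8.1.1 | No |
| PGI-C improvement | Number and percentage | No |

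Several exploratory endpoints in SAP 8.5.3 (EQ-VAS, WPAI, PROMIS Fatigue) are also assigned ANCOVA. The PGI endpoints therefore get less inference than lower-ranked ones.

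**Step 2. Does another section supply the method?** No.

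- Protocol 9.4.3 names longitudinal models or ANCOVA, but only for change in continuous endpoints. It gives nothing for a binary endpoint.
- SAP 8.1.7 states the pairwise principle without a method.
- SAP 5.1 lists treatment, time and the baseline value as model terms, but names no model for a binary or ordinal outcome.

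**Step 3. The plan's own figure.** Inputs from SAP 4.3: 95 per group, 10% dropout, difference 1, SD 2.2, two-sided alpha 0.05.

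- Evaluable per arm: 95 × 0.9 = 85.5
- SE = 2.2 × √(2/85.5) = 0.336
- Power = Φ(1/0.336 − 1.96) = Φ(1.01) = 84.4%

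The stated 84% reproduces, so 85.5 per arm is a fair basis for the illustration.

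**Step 4. Precision of a PGI comparison (illustration).** The documents give no PGI response rates. The assumption is a placebo rate p₀ of 30% to 60% and an active rate p₁ that is 10 to 25 points higher.

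- 95% half-width = 1.96 × √[(p₀(1−p₀) + p₁(1−p₁))/85.5]
- p₀ = 0.40, p₁ = 0.50: 1.96 × √(0.49/85.5) = 0.148
- p₀ = 0.60, p₁ = 0.85: 1.96 × √(0.3675/85.5) = 0.128
- Range over the whole grid: 0.128 to 0.148, or about 13 to 15 points

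Under the same assumptions, power at two-sided 0.05 is:

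| Difference | Power |
|---|---|
| 10 points | 26–28% |
| 15 points | 50–55% |
| 20 points | 75–82% |
| 25 points | 91–96% |

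With assumed rates of 50% and 40%, the observed gap of 10 points would have a 95% CI of about −5 to +25. The planned tables would show the 10 but not the interval.

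**The case against.** A good case can be made for description.

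- **Wording of the objectives.** Objectives 1 to 3 name placebo; 5 and 6 speak only of evaluating change at different time points. The PGI-C endpoint is itself a percentage, and 8.4.3 delivers it by treatment group and visit.
- **General rules.** Protocol 9.1 provides for frequency and percent for categorical variables where appropriate, SAP 8.1.1 does the same for categorical and ordinal ones, and protocol 9.4.3 commits to models only for continuous endpoints.
- **Stakes.** This is a phase 2a/b trial with nominal p-values, and SAP 4.2 sets formal hypotheses for the primary endpoint only.

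Part of this stands. A reader might infer that no treatment comparison is produced at all, or that two secondary objectives cannot be answered. That goes too far: the arms are tabulated side by side, and counts with denominators let a reader work out a crude interval. A reader might also infer that PGI-S improvement has no output. It has counts under 8.1.1, and improvement of at least one step can be read from the shift table. Nor do the documents say that a method will be chosen after unblinding; they say only that unplanned analyses must be identified.

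The wording argument does not remove the gap. Objectives 4 (rescue medication) and 7 (EHP-30) also omit placebo from their own text, yet the SAP models both against placebo. The shared Table 1 header and protocol 9.1.1 cover PGI-S change and PGI-C in the same way, and nothing marks the PGI endpoints as descriptive only.

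**Conclusion.** The point holds as an internal inconsistency: Table 1 and protocol 9.1.1 announce a tested comparison with placebo, and SAP 8.4.3 specifies only descriptive output, while section 10 declares no change. What is missing is a prespecified inferential comparison, not the data or the tabulation. For the added PGI-S improvement variable the argument is weaker, because it is not in Table 1 and the header does not reach it directly; protocol 9.1.1 and SAP 8.1.7 still bear on it as a secondary variable.

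No figure in the documents changes. The half-width of 13 to 15 points rests on the assumed rates and on 10% dropout applying to the PGI assessments. The priority is moderate: the primary endpoint is untouched and all p-values are nominal.

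**What to change.** In SAP 8.4.3, before unblinding, add for improvement on PGI-C and on PGI-S at TRC1, TRC2 and TRC3:

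- each dose against placebo as a difference in proportions with 95% CI and nominal p-value;
- one named method, for example logistic regression with baseline PGI-S as covariate and a standardised risk difference;
- the MFAS with observed data and a stated denominator, including how women with a baseline PGI-S of 0 are counted, since they cannot improve by a step;
- TRC3 as the main time point, with the PGI-S shift table kept as descriptive support.

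The work is a few sentences and two output tables on data the trial already collects. The cost is up to 2 variables × 3 doses × 3 cycles = 18 further unadjusted comparisons, which is why TRC3 should be named as the main one.

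If the sponsor intends the PGI endpoints to be descriptive only, the cheaper change is to say so in section 10 as a departure from protocol 9.1.1, and to align the Table 1 header.

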#### ANALYSIS OF EHP-30

The five EHP-30 Domain scores will be summarized by descriptive statistics of observed data and change from baseline values.

A similar analysis for the primary efficacy variable described in Section 8.3.7 using ANCOVA will be performed for change from baseline in each EHP-30 Domain score.

### 8.5. Analyses Supporting Exploratory Efficacy Objectives

#### 8.5.1. Exploratory Efficacy Endpoints

##### ENDOMETRIOSIS-RELATED PAIN (DYS, NMPP, OPP) SCORES

The exploratory efficacy endpoints for endometriosis-related pain scores are:

- Change from BC to TRC1 of the mean OPP score
- Change from BC to TRC1 of the mean DYS score

- Change from BC to TRC1 of the mean NMPP score
- Change from BC to TRC2 of the mean OPP score
- Change from BC to TRC2 of the mean DYS score
- Change from BC to TRC2 of the mean NMPP score
- Change from SC to SFC of the mean OPP score
- Change from SC to SFC of the mean DYS score
- Change from SC to SFC of the mean NMPP score

Change from SC to SFC of the score where means for a cycle will be calculated if there is at least one CCI score is reported within each of these cycles.

#### EUROQOL-5 DIMENSIONS 5-LEVEL VERSION (EQ-5D-5L)

The EQ-5D-5L consists of the EQ-5D descriptive system and the EQ Visual Analog Scale (EQ-VAS). The descriptive system consists of five dimensions: mobility, self-care, usual activities, pain/discomfort, and anxiety/depression. Each dimension has five levels: no problems, slight problems, moderate problems, severe problems, unable to/extreme problems. The participant is asked to indicate her health state in the eDiary by ticking the box next to the most appropriate statement in each of the five dimensions. This decision results in a 1-digit number that expresses the level selected for that dimension. The digits for the five dimensions are combined into a digit number that describes the participant's health state. The EQ-VAS records the participant's self-rated health on a vertical VAS where the anchors are labeled 'Best health you can imagine' and 'Worst health you can imagine'.

The following EQ-5D-5L exploratory efficacy endpoints will be evaluated:

- Change from CCI (BC) to CCI (TRC3) in EQ-VAS
- Change from CCI (BC) to CCI (TRC3) in each of the five dimensions

#### INTERFERENCE WITH DAILY ACTIVITIES

Participants will complete eDiary items asking about any interference with daily activities over the last 24 hours on 11-point NRS. The NRS measures the level of interference 0 (not difficult) to 10 (extremely difficult) where lower value represents a better outcome.

The following exploratory efficacy endpoint will be evaluated:

- Mean change from BC to TRC3 in level of difficulty to do daily activities

The mean level of difficulty to do daily activities will be calculated for each cycle as the total of level of difficulty to do daily activities scores reported during the cycle divided by the number of days during the cycle in which the score was reported. The mean level of difficulty to do daily activities score for a cycle will be calculated if there is at least one level of difficulty to do daily activities score reported within that cycle.

#### WPAI-ENDOMETRIOSIS

The WPAI-Endometriosis is a PRO instrument that measures the effect of endometriosis on work productivity and daily tasks. The WPAI-Endometriosis questionnaire contains six items (Q1-Q6) that produce four different scale scores. WPAI outcomes are expressed as impairment percentages, with higher numbers indicating greater impairment and less productivity. The scoring algorithms for the four WPAI: Endometriosis scales are as follows:

1. Absenteeism (% work time missed due to endometriosis) =  $\frac{Q2}{Q2+Q4} \times 100$ ;
2. Presenteeism (% impairment while working due to endometriosis) =  $\frac{Q5}{10} \times 100$ ;
3. Work productivity impairment (% work impairment due to endometriosis) =  $[\frac{Q2}{Q2+Q4} + ((1 - \frac{Q2}{Q2+Q4}) \times \frac{Q5}{10})] \times 100$ ; and
4. Daily activity impairment (% activity impairment due to endometriosis) =  $\frac{Q6}{10} \times 100$ .

Note. If Q4=0, Q5 will be missing from the questionnaire and should be replaced by 0 in the calculation; If Q2=0 and Q4=0, Absenteeism will be defined as 0.

The WPAI-Endometriosis diary is completed during CCI and CCI EOT.

The following WPAI-Endometriosis exploratory efficacy endpoints will be evaluated:

- Mean change from CCI (baseline) to CCI EOT in absenteeism
- Mean change from CCI (baseline) to CCI EOT in presenteeism
- Mean change from CCI (baseline) to CCI EOT in work productivity impairment
- Mean change from CCI (baseline) to CCI EOT in daily activity impairment

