#### ANALYSIS OF WPAI-ENDOMETRIOSIS

Similar analyses as for the primary efficacy variable described in Section 8.3.7 using ANCOVA will be performed for the WPAI-Endometriosis exploratory efficacy endpoints.

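### The WPAI scoring note gives presenteeism its best score, 0%, to a woman who worked no hours, although the scale is undefined for her

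*SAP*

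**What the plan says.** SAP 8.5.1 (WPAI-Endometriosis) derives four percentage scores, "with higher numbers indicating greater impairment and less productivity". Three concern work:

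- "Absenteeism (% work time missed due to endometriosis") is Q2/(Q2+Q4) × 100.
- "Presenteeism (% impairment while working due to endometriosis") is Q5/10 × 100.
- "Work productivity impairment (% work impairment due to endometriosis"), called the composite below, is [Q2/(Q2+Q4) + (1 − Q2/(Q2+Q4)) × Q5/10] × 100.

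The fourth, daily activity impairment, uses Q6 alone.

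A note placed after all four formulas gives two rules: "If Q4=0, Q5 will be missing from the questionnaire and should be replaced by 0 in the calculation"; and "If Q2=0 and Q4=0, Absenteeism will be defined as 0". Neither rule is tied to a particular scale beyond its own wording.

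Presenteeism is an endpoint in its own right: the list of change endpoints includes the change from baseline to "EOT in presenteeism". SAP 8.5.3 says that "ANCOVA will be performed for the WPAI-Endometriosis exploratory efficacy endpoints", following SAP 8.3.7, where the baseline value is the covariate. SAP 8.1.5 (general) and SAP 8.5.2 (exploratory endpoints) both exclude imputation of missing data.

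**The concern.** Presenteeism measures how far endometriosis hampers a woman during the hours she works. With no hours worked there is nothing to measure, and the note itself describes Q5 as missing. Replacing it by 0 does not leave the scale neutral: it assigns the most favourable value possible. A woman who lost all her work time to endometriosis then has the same presenteeism score as one who worked full hours without difficulty.

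Because presenteeism is analysed separately as a change from baseline, a false zero at end of treatment appears as improvement and a false zero at baseline as worsening. A false baseline zero also enters the ANCOVA as a covariate value. Hours worked at end of treatment are measured after randomisation and may be affected by treatment, so the false zeros need not be balanced between arms.

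**Working it through.** **Inputs.** The formulas and both rules are from SAP 8.5.1. The SAP does not print the item wording; that Q2 is hours missed because of endometriosis and Q4 is hours worked is inferred from the absenteeism formula. The hours and Q5 values below are illustrative. The plan gives no sample size or expected value for the WPAI, so it has no figure to reproduce.

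**Step 1: single cases.**

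| Case | Q2 | Q4 | Q5 | Absenteeism | Presenteeism | Composite |
|---|---|---|---|---|---|---|
| A. Full hours, hampered | 0 | 40 | 8 | 0% | 80% | 80% |
| B. All hours missed | 40 | 0 | set to 0 | 100% | 0% | 100% |
| C. Full hours, not hampered | 0 | 40 | 0 | 0% | 0% | 0% |
| D. No hours worked or missed | 0 | 0 | set to 0 | 0% by rule | 0% | 0% if the absenteeism value is carried in |

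- B and C have the same presenteeism score.
- From A at baseline to B at end of treatment, absenteeism changes by +100 points, the composite by +20 and presenteeism by −80. The first two move in the right direction; presenteeism alone reverses.
- The reverse also occurs. From B at baseline to Q2=0, Q4=40, Q5=3 at end of treatment, absenteeism goes from 100% to 0% and the composite from 100% to 30%, but presenteeism goes from 0% to 30%, a false worsening.

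**Step 2: where the substitution does no harm.** In case B the weight on Q5 in the composite is 1 − 40/40 = 0. Q5 = 0, 5 or 10 all give 100%. The substitution is needed there only so that the formula can be evaluated.

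**Step 3: no hours of either kind.** In case D, Q2/(Q2+Q4) is 0/0. The note fixes absenteeism at 0% and, through Q5, presenteeism at 0%. It does not say what the composite should be.

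**Step 4: effect on an arm mean.** If a share f of an arm has Q4=0 and the remaining women average m, the mean with false zeros is m(1 − f), a fall of f × m. The documents give neither quantity, so these are assumptions:

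| m | f = 2% | f = 5% | f = 10% | f = 20% |
|---|---|---|---|---|
| 30% | 0.6 | 1.5 | 3.0 | 6.0 |
| 50% | 1.0 | 2.5 | 5.0 | 10.0 |
| 70% | 1.4 | 3.5 | 7.0 | 14.0 |

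**Step 5: effect on the contrast with placebo.** These are comparisons of unadjusted end-of-treatment means. If f is equal in both arms and unrelated to the score, the difference shrinks by the factor (1 − f): a 10-point difference becomes 9.5 at f = 5%. If m = 50% in both arms but f is 5% in one and 10% in the other, the means are 47.5 and 45.0, a spurious 2.5 points in favour of the arm with more women not working.

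**The case against.** The strongest defence is that the author meant the substitution for the composite only, where Step 2 shows it is harmless when Q2>0. That may be so, but the note follows all four formulas without such a limit, and a programmer following it would code presenteeism as 0%.

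It can also be said that this is a scoring convention and not imputation. The note, however, calls Q5 missing and supplies a value, so SAP 8.1.5 and 8.5.2 at least need reconciling with it.

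On scope the objections stand. A reader might infer that a woman too ill to work is recorded as unimpaired at work altogether. The SAP's formulas do not support that: with Q2>0 and Q4=0, absenteeism and the composite both show 100%, so only presenteeism is affected. A reader might also infer that the plan sets all three work scales to 0% when Q2=Q4=0. It states this for absenteeism, and it follows for presenteeism; for the composite it is a plausible inference about an undefined case. Nor does the SAP section give a recall period, say how Q1 is used, or say whether women without paid work are left out of the work scales.

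Finally, scoring as missing has a price. Dropping women who could not work makes missingness depend on outcome, and with WPAI change defined only from baseline to end of treatment there is no intermediate value to carry forward under the second analysis in SAP 8.3.7.

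**Conclusion.** The point holds for presenteeism. As written, the note assigns the best score where the scale is undefined, on a separately analysed endpoint, and this can reverse the sign of an individual change. The handling of Q2=Q4=0 is also unsound for absenteeism and incomplete for the composite.

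The individual effect follows directly from the SAP's formulas: 80 points in the worked example. The group effect rests on assumption: a fall of 0.6 to 14 points in an arm mean for 2–20% of women with Q4=0 and a mean of 30–70% in the others. The documents do not allow the size or direction of bias in the contrast with placebo to be stated, because that depends on the share in each arm at each visit.

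The consequence is limited. The endpoint is exploratory, p-values are nominal, and neither daily activity impairment nor any primary or secondary analysis is touched.

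**What to change.** Replace the note in SAP 8.5.1 with scale-specific rules:

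- Presenteeism: missing if Q4=0.
- Absenteeism and work productivity impairment: missing if Q2+Q4=0.
- Work productivity impairment when Q2>0 and Q4=0: use Q5=0 inside the formula only, which gives 100%.
- Daily activity impairment: unchanged.

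State also whether women without paid work contribute to the work scales. These rules agree with SAP 8.1.5 and 8.5.2 as they stand.

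The cost is a few lines of text, no new data, and some more missing values; how many cannot be judged from the documents. The presenteeism comparison is then restricted to women who worked at both visits, so it should be reported with the number excluded per arm and read together with absenteeism and the composite.
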